10.2.12. Number of Cigarettes Smoked Over Time

The number of cigarettes smoked will be collected every week from Week 2 to Week 12, then at Week 16, Week 20, and Week 24.

The treatment arms will be compared (cytisinicline 6 weeks vs placebo, cytisinicline 12 weeks vs placebo) using repeated-measures analysis of variance models with fixed effect terms for treatment arm, visit and visit * treatment arm interaction. The between-arm difference in means, their respective 95% CIs and Bonferroni-adjusted p-values will be reported. A figure for the number of cigarettes smoked by treatment arm and visit will be provided for the All Randomized Set.

An additional analyses will be performed by abstinence status for the primary endpoint (Weeks 3 – 6 and Weeks 9 -12).

10.3. Other Analyses Not Specified

Other analyses not detailed in this SAP are anticipated and will be conducted by an independent statistician ([name]; TriArc Consulting). These analyses fall into the class of being “data-directed” and will be labeled as such. Explanations of objectives, details of methodology, identification of limitations, any known/anticipated biases, and known/anticipated threats to validity will accompany each analysis. Here are examples:

- Additional sensitivity analyses that have the potential to provide alternative explanations for observed between-arm differences or lack thereof.
- Analyses of observed trial conduct anomalies and the relationship of these to understanding the observed results.
- Fitting of multiple explanatory variable models of outcomes including and especially including interactions.
- Analyses designed to explore the associations between outcomes.
- Analyses designed to explore the relationship between safety and efficacy.
- Analyses illustrating consistency across multiple outcomes measures.

11. SAFETY ANALYSIS

Safety objectives are described in Section 3.4. All safety analyses described below will be presented for each treatment arm using the Safety Set (see Section 6.5).

Safety analyses that are presented “by visit” will include a derived visit named EOT (see Section 4.2.1.4). This includes summaries of hematology and serum chemistry test results, vital signs, weight, and 12-lead ECG results.

No statistical comparisons between treatment arms are planned for safety endpoints; thus, no statistical test results will be reported.

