In addition, the study will compare the safety profiles of 3 mg TID dosing for 6 weeks (Arm B) and 12 weeks (Arm C), relative to placebo (Arm A).

Objectives:

Multiple Primary Efficacy Objectives:

The multiple primary objectives are based on two comparisons where study success can be based on success for either comparison:

1. Assess whether subjects randomized to Arm B (3 mg cytisinicline TID for 6 weeks followed by placebo TID for 6 weeks plus behavioral support) have a higher probability of abstinence from Week 3 to Week 6 post-randomization as compared to subjects randomized to Arm A (placebo TID plus behavioral support).
2. Assess whether subjects randomized to Arm C (3 mg cytisinicline TID for 12 weeks plus behavioral support) have a higher probability of abstinence from Week 9 to

Week 12 post-randomization as compared to subjects randomized to Arm A (placebo TID plus behavioral support).

Secondary Efficacy Objectives:

The analysis for secondary objectives 1 and 2 will be done only if the corresponding primary comparison passes statistical criterion.

1. Assess whether subjects randomized to Arm B (3 mg cytisinicline TID for 6 weeks followed by placebo TID for 6 weeks plus behavioral support) have a higher probability of continuous abstinence from Week 6 to Week 24 post-randomization as compared to subjects randomized to Arm A (placebo TID plus behavioral support).
2. Assess whether subjects randomized to Arm C (3 mg cytisinicline TID for 12 weeks plus behavioral support) have a higher probability of continuous abstinence from Week 12 to Week 24 post-randomization as compared to subjects randomized to Arm A (placebo TID plus behavioral support).

The analysis for secondary objective 3 will be conditional and performed only if both primary comparisons 1 and 2 pass statistical criterion.

3. Assess for a reduction in risk of relapse from Week 6 to Week 24 in subjects receiving 3 mg cytisinicline for 6 weeks and then either continue 3 mg cytisinicline from Week 6 to Week 12 (Arm C) or were switched to placebo from Week 6 to Week 12 (Arm B). Subjects not abstinent at Week 6 will be regarded as having relapsed.

Other Objectives:

1. To compare arms (Arm B vs Arm A; Arm C vs Arm A) on 7-day point prevalence abstinence weekly at Week 2 to Week 12, then for Weeks 16, 20, and 24.
2. To compare arms (Arm B vs Arm A; Arm C vs Arm A) on serum cotinine levels every other week at Week 2 to Week 12, then at Weeks 16, 20, and 24.

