3.4. Safety Objectives

1. To evaluate the safety profile of 3 mg TID cytisinicline compared to placebo (Arm B vs Arm A; Arm C vs Arm A).
2. To compare the safety profiles of Arm B subjects versus Arm C subjects with respect to adverse events occurring after Week 6 on the study.

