6.2. General Considerations

Statistical analyses will be performed at the end of the study after the last subject has completed the Week 24 visit, all data have been reported, cleaned, and the eCRF database has been locked.

Medical history events and adverse events will be coded to standard “preferred terms” and “system organ classifications (SOC)” using the Medical Dictionary for Regulatory Activities (MedDRA) Version 23.1 or higher. Concomitant medications will be coded using the World Health Organization Drug Dictionary (WHODrug) Version Mar-2021 B2 or higher.

All statistical programming will be done using SAS® Version 9.4 or higher (SAS® Institute, Cary, North Carolina). All tables, figures and listings will be produced in landscape format.

In general, all data will be listed by treatment arm, subject and visit/time point where appropriate. The summary tables will have columns corresponding to, or be stratified by, treatment arm. In listings and summary tables the treatment arms will be ordered and labelled as follows: Placebo, Cytisinicline 6 Weeks, Cytisinicline 12 Weeks.

The total number of subjects under the stated analysis set in each treatment arm (N) will be displayed in the header of summary tables.

Data will be summarized using descriptive statistics for continuous variables. Unless otherwise specified, descriptive statistics will include number of subjects (n), mean, standard deviation, minimum, median and maximum. In case of $n < 2$, where n indicates the number of subjects with evaluable data at the particular time point, the standard deviation will be empty. The statistic “Missing” will also be presented as the number of missing entries/subjects, if any at that visit/timepoint, and presented as a summary statistic only when non-zero. The minimum and maximum statistics will be presented to the same number of decimal places as the original data. The mean and median will be presented to one more decimal place than the original data, whereas the standard deviation will be presented to two more decimal places than the original data.

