6.5. Analysis Sets

Three analysis sets will be used.

Screening Set: all subjects who give written informed consent and enter screening. The Screening Set consists of two mutually exclusive subgroups:

- subjects who were not randomized at completion of screening, generally due to failure of one or more of the study entry criteria (ie, the inclusion/exclusion criteria) and
- subjects who were randomized at completion of screening

All Randomized Set: all randomized subjects. Subjects will be evaluated by their randomized treatment arm ('intent-to-treat' analysis) unless otherwise specified. The All Randomized Set will be the primary set for efficacy analyses.

Safety Set: all randomized subjects who take at least one dose of study drug. Subjects will be evaluated by their randomized treatment arm ('intent-to-treat' analysis) unless otherwise specified. The Safety Set will be the primary set for safety summaries. Safety summaries may also be provided based on the treatment actually received.

Achieve will approve the list of subjects to be excluded from the Safety Set after database lock. Achieve must approve this list before any analysis is to be performed.

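### The safety objectives compare arms, but the SAP gives only by-arm percentages with no estimate or interval, and its after-Week-6 tables lack an at-risk set and a usable start date for subjects who stopped drug early

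*SAP*

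**What the plan says.** Protocol 6.4 and SAP 3.4 give the same two safety objectives. The first sets Arm B and Arm C each against placebo. The second reads: "To compare the safety profiles of Arm B subjects versus Arm C subjects with respect to adverse events occurring after Week 6 on the study". On method, SAP 11 states: "No statistical comparisons between treatment arms are planned for safety endpoints; thus, no statistical test results will be reported".

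Protocol 16.7 says that safety variables will be summarized and leaves the summaries to the SAP. SAP 11.1 provides them as counts and percentages by arm. Several address the second objective: two overall after-Week-6 tables, after-Week-6 tables by system organ class and preferred term and for events leading to dose reduction or discontinuation, a table for the Week 6 to Week 7 window, and a time-of-onset table. None carries a risk difference, a ratio or a confidence interval.

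On the denominator, SAP 11 says: "All safety analyses described below will be presented for each treatment arm using the Safety Set". SAP 6.5 defines that set as "Safety Set: all randomized subjects who take at least one dose of study drug", and SAP 6.2 adds: "The total number of subjects under the stated analysis set in each treatment arm (N) will be displayed in the header of summary tables". SAP 6.2 also defines a percentage as n/M, where M counts subjects with a non-missing value, but it does not say what M is for adverse events.

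On timing, SAP 11.1 counts an event as after Week 6 if it starts later than the date of the Week 7 Day 1 dose. A second version adds events still ongoing on that date. Dosing dates come from the treatment diaries. SAP 4.2.1.4 expects subjects who stop treatment early to stay in the study to Week 24.

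**The concern.** An objective worded as a comparison needs a comparative quantity, and none is specified for safety. SAP 10.2.2, 10.2.3 and 10.2.12 do specify between-arm differences with 95% intervals for cotinine, expired CO and cigarette counts, which are exploratory. A numbered safety objective therefore gets less than an exploratory endpoint.

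The B versus C question belongs to the design rationale. Protocol 7.3.2 raises the possibility that the shorter regimen is safer because exposure is shorter, and events after Week 6 in B and C are the randomized evidence on that. Two bare percentages do not show whether a gap of a few points is informative.

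The after-Week-6 tables raise two further questions: who is in the denominator, and how an event is classified when the subject never took the dose that starts the clock.

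**Working it through.** **Inputs.** There are 250 subjects per arm (SAP 2.2). The documents give no expected adverse event risk and no share of subjects gone by Week 7, so both are assumptions below, shown over a range. The nearest figure is the 5% trigger in SAP 5.3, which concerns stopping treatment before Week 6 for reasons other than adverse events. It is not a rate of leaving the study.

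**The plan's own figure.** The only sizing figure is the 95.7% power for each primary efficacy comparison. Exact enumeration of one-sided Fisher tests (250 per arm, 7% versus 19%, level 0.0125) gives 95.75%, so it reproduces. It has no bearing on safety.

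**Precision that is not reported.** With equal risk p in both arms, the 95% half-width is 1.96 × √(2p(1−p)/250).

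| p | 2p(1−p)/250 | Half-width (points) |
|---|---|---|
| 2% | 0.000157 | 2.5 |
| 5% | 0.000380 | 3.8 |
| 10% | 0.000720 | 5.3 |
| 20% | 0.001280 | 7.0 |

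As a reference point, Protocol Table 3 (ORCA-1) shows abnormal dreams, nausea, insomnia and constipation each at 6.0% in the 3 mg TID arm. That was a 25-day study. At p = 6% the half-width is 1.96 × √(0.1128/250) = 4.2 points, about two thirds of the rate itself.

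**Denominator.** Let d be the share of the Safety Set no longer observed at Week 7, and p the after-Week-6 risk among the rest. Dividing by the full Safety Set shows p × (1−d). Take assumed true risks of 10% in B and 15% in C, with equal d in both arms:

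| d | Shown B / C | Shown difference (points) | True difference (points) | Half-width on at-risk subjects (points) | Ratio C:B |
|---|---|---|---|---|---|
| 5% | 9.50% / 14.25% | 4.75 | 5.0 | 5.9 | 1.50 |
| 10% | 9.00% / 13.50% | 4.50 | 5.0 | 6.1 | 1.50 |
| 15% | 8.50% / 12.75% | 4.25 | 5.0 | 6.3 | 1.50 |
| 20% | 8.00% / 12.00% | 4.00 | 5.0 | 6.5 | 1.50 |

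The half-width here is 1.96 × √((0.10×0.90 + 0.15×0.85)/(250(1−d))). Dilution removes 0.25 to 1.0 point, against an uncertainty of about 6 points.

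**Could d differ between B and C?** Both arms take the same blinded active drug to Week 6 (Protocol 7.2), so only chance separates them. With d of 10% in B and 15% in C, the shown difference is 0.15×0.85 − 0.10×0.90 = 3.75 points and the ratio is 1.42. With 10% and 20%, it is 0.15×0.80 − 0.10×0.90 = 3.0 points and the ratio is 1.33. The second case is extreme: around a common 15%, the standard error of the difference in d is √(2×0.15×0.85/250) = 3.2 points, so a 10-point gap is about three standard errors.

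**Anchor date.** Week 7 Day 1 is Study Day 6×7 + 1 = 43. A subject who stopped drug before then has no Week 7 Day 1 dose. SAP 4.2.1.4 keeps that subject in follow-up and SAP 11.1 collects events to Week 24, but no rule says whether the subject's later events fall before or after Week 6. Changing the denominator alone to subjects still in the study would bring in people whose events cannot be classified.

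**The case against.** The strongest reply is that the protocol planned descriptive safety reporting and the SAP delivers it. Protocol 16.7 promises summaries, so there is no conflict between the documents. Avoiding p-values for safety is reasonable, and no efficacy conclusion or alpha is affected. Each table gives n, % and N, so a reader can compute an interval. The half-widths above describe precision, which adding an interval does not improve. All of this stands.

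Four stronger readings are tempting, and the documents do not support them:

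- That SAP 11 forbids any comparison. It rules out statistical comparisons and tests; side-by-side tables for the after-Week-6 question remain.
- That the SAP states division by everyone ever treated. This is the natural reading of SAP 11, 6.5 and 6.2 together, but M is left open for adverse events.
- That the denominator biases B against C. The factor is equal in expectation and leaves the ratio unchanged. Leaving could differ between placebo and active arms, but the after-Week-6 objective concerns B and C only.
- That the safety sentence in the synopsis rationale asks for B versus C. Read to its end, it sets each regimen against placebo. The B versus C question rests on Protocol 6.4 and SAP 3.4.

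The reply does not remove the need for a prespecified estimate. A reader can rebuild an interval only if the denominator and event classification are clear, and for the after-Week-6 tables they are not.

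**Conclusion.** The point holds as a low-cost improvement to the safety reporting. Two comparative objectives have no comparative estimate or interval. At 250 per arm the unreported half-width is about 3.8, 5.3 and 7.0 points at assumed risks of 5%, 10% and 20%, and somewhat wider on a smaller at-risk set (7.0/√0.85 = 7.6 points at 20% risk if 15% have gone).

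The denominator effect is secondary: a factor of 1−d, with d not given in the documents, equal in expectation for B and C. It rests on reading the Safety Set as the divisor. The missing anchor needs no such assumption. As written, SAP 11.1 cannot classify later events in subjects who stopped drug before Week 7 and stayed in the study.

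**What to change.** In SAP 11 and 11.1, add descriptive risk differences with 95% score intervals and no p-values: B−A and C−A over the whole study, and C−B after Week 6. Apply them to any TEAE, serious adverse events, TEAEs leading to dose reduction or discontinuation, and preferred terms above a frequency threshold stated in the SAP before unblinding. Amend the SAP 11 sentence so that it excludes hypothesis tests only.

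For the after-Week-6 tables:

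- Use subjects still in the study at the start of Week 7 as the denominator, and state that this is M.
- Keep the Week 7 Day 1 dose date as the anchor where it exists, and set a calendar anchor, for example the Study Day 43 equivalent, for subjects without that dose.
- Show the full Safety Set percentage as a footnote.

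The cost is SAP wording and extra columns in tables already planned, with no new data, visits or alpha. Displayed after-Week-6 percentages will rise slightly.

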11.1. Adverse Events

Per the study protocol all adverse events (AE) occurring during the study, whether or not attributable to study drug, will be recorded in the subject’s source documents and CRF. The adverse event reporting period will start at the date of informed consent and continue through the end of the study (Week 24 visit). Treatment emergent adverse events (TEAE) are defined in Section 4.2.1.

AE severity will be assessed by the Investigator as mild, moderate or severe. The Investigator will also assess the relationship of each AE to study drug (none, unlikely, possible, probable, definite). Treatment-related AEs are defined as events the Investigator considers to be possibly, probably, or definitely related to study drug, as well as events with “unknown” relationship.

Adverse event summaries will present data for the 3 treatment arms. An overall summary of adverse events will be provided that reports, for each treatment arm, both the number (%) of events meeting a specific criterion and the number (%) of subjects with at least one event meeting that criterion during the AE reporting period. Events meeting the following specific criteria will be presented in this table:

- Any reported adverse event (ie, both pre-existing and treatment-emergent events)
- For treatment-emergent AEs:
 - Any TEAE
 - Any serious TEAE
 - Any related serious TEAE
 - TEAEs by severity (mild, moderate, severe)
 - TEAEs by relationship (none, unlikely, possible, probable, definite)
 - TEAEs by relationship (not related, related)
 - TEAEs by action taken with study drug (dose not changed, dose reduced, dose interrupted, drug withdrawn, not applicable, unknown)
 - TEAEs by outcome (Fatal, Not recovered/Not resolved, Recovered/Resolved, Recovered/Resolved with sequelae, Recovering/Resolving)

Three overall summary tables will be provided, as follows:

- all AEs during the study
- all AEs occurring after Week 6 on the study, defined as AEs with start date after the date of the Week 7 Day 1 dose.
- All AEs occurring after Week 6 of the study defined as AEs with start date after the date of the Week 7 Day 1 dose, or AEs that are ongoing (ie, not resolved) on the date of the Week 7 Day 1 dose.

Dosing dates will be obtained from subject treatment diaries.

In addition to the overall summaries described above, the following summaries of TEAEs occurring anytime during the study will be produced:

- Incidence by SOC and preferred term (PT), in alphabetical order of SOC and PT, for both all TEAE and related TEAE
- Incidence by PT, in decreasing frequency of PT, for both all TEAE and related TEAE
- Incidence of TEAEs that resulted in dose reduction or discontinuation of study drug (ie, action taken with study drug reported as dose reduced, dose interrupted, or drug withdrawn), in decreasing frequency of PT
- Incidence of TEAE by PT and severity (mild, moderate, severe), in alphabetical order of PT

- Incidence of TEAE by PT and relationship (related, not related), in alphabetical order of PT
- Incidence of TEAE by PT for events of special interest: COVID-19

The following summaries will also be produced of TEAEs occurring after Week 6 (occurring after Week 6 or ongoing after Week 6) on the study (see definitions above):

- Incidence by SOC and PT, in alphabetical order of SOC and PT
- Incidence by PT, in decreasing frequency of PT
- Incidence of TEAEs that resulted in dose reduction or discontinuation of study drug (ie, action taken with study drug reported as dose reduced, dose interrupted, or drug withdrawn), in decreasing frequency of PT

The following will also be summarized:

- Incidence of TEAEs that occurred from Week 6 (approximately Study Day 42) visit + 1 day through Week 7 visit (approximately Study Day 49) will be assessed for any possible withdrawal effects when switching to placebo during the first Week 7 timeframe for the cytisinicline 6 weeks arm.
- Incidence of TEAEs by time of onset (Up to Week 6 [approximately Study Day 42] visit and after Week 6 visit through Last Dose)
- Incidence of TEAEs by primary endpoint status

In summaries of AE incidence, if a subject experiences the same AE (preferred term) multiple times that subject will be counted only once for that preferred term. Similarly, if a subject experiences multiple AEs (preferred terms) within the same SOC then that subject will be counted only once for that SOC. When summarizing by severity and relationship, only the AE with the highest severity or relationship will be counted.

A Kaplan-Meier figure of time to first TEAE (ie, time from date of randomization to earliest TEAE start date) will be provided by treatment arm. Subjects with no Adverse events will be censored at their last visit.

In addition to summary tables, the following listings will be produced.

- All AEs
- AEs which resulted in dose reduction or discontinuation of study drug (ie, action taken with study drug reported as dose reduced, dose interrupted, or drug withdrawn)

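### The onset-only after-Week-6 adverse event tables leave out the switch day, and no after-Week-6 rule covers subjects without a Week 7 Day 1 dose

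*SAP*

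**What the plan says.** The second safety objective in SAP Section 3.4 reads: "To compare the safety profiles of Arm B subjects versus Arm C subjects with respect to adverse events occurring after Week 6 on the study".

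Section 11.1 gives two definitions of the period. The first is by onset only: "defined as AEs with start date after the date of the Week 7 Day 1 dose". The second takes the same events and adds those already present: "or AEs that are ongoing (ie, not resolved) on the date of the Week 7 Day 1 dose". On the source of the cut-off it says: "Dosing dates will be obtained from subject treatment diaries". The tables by system organ class and preferred term, and the table of events leading to dose reduction or discontinuation, refer back to both definitions: "TEAEs occurring after Week 6 (occurring after Week 6 or ongoing after Week 6) on the study (see definitions above").

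The same section adds two summaries tied to visits. One looks for withdrawal effects after the switch: "Incidence of TEAEs that occurred from Week 6 (approximately Study Day 42) visit + 1 day through Week 7 visit". The other splits events at the Week 6 visit and ends at the last dose.

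**The concern.** Under Protocol Section 7.2, Arm B takes cytisinicline for six weeks and then placebo. The date of the Week 7 Day 1 dose, nominally Study Day 43, is therefore the first day on which Arms B and C differ. A rule that requires a later calendar date excludes every event starting that day, including one that begins after the first Week 7 tablet.

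The rule also assumes that everyone has such a dose. A subject who stopped earlier, or who missed that dose, has no cut-off. Their events cannot be placed before or after Week 6 by anything written in the SAP, so the counts would depend on an unstated programming choice.

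**Working it through.** The documents state no figure for events after Week 6, so there is nothing to reproduce. The check compares the rules and then counts days and subjects.

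**1. Switch day, comparison of rules**
- SAP Section 4.2.1.1 (treatment emergence at first dose): inclusive, using date and time.
- SAP Section 11.1, onset-only: strict, using date alone.
- SAP Section 11.1, onset or ongoing: keeps a switch-day event that is unresolved on that date. It is unclear for one that resolves the same day.
- Times are available for both sides of the comparison: Protocol Section 14.2 records the time of AE onset, and SAP Section 6.1 lists diary dates and times for each dose. Nothing forces the stricter rule.

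**2. Switch day, size**

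Share lost = 1 / L, where L is the length of the window in days and onset is assumed uniform.
- Week 7, Days 43-49: L = 49 - 43 + 1 = 7; 1/7 = 14.3%.
- Second treatment period, Days 43-84: L = 42; 1/42 = 2.4%.
- To Week 24, Days 43-168: L = 126; 1/126 = 0.8%.

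With an assumed 100 events per arm, this is 100/126 = 0.8 to 100/42 = 2.4 events.

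If the switch-day rate were m times that of other days (assumption), the share would be m / (m + L - 1). For m = 3 to 5:
- Week 7: 3/9 = 33% to 5/11 = 45%.
- Days 43-84: 3/44 = 6.8% to 5/46 = 10.9%.
- Days 43-168: 3/128 = 2.3% to 5/130 = 3.8%.

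**3. Subjects without a cut-off, comparison of rules**
- SAP Section 4.2.1.4 expects those who stop treatment early to remain until Week 24, so they can have events after Week 6.
- SAP Section 6.1 shows that the diary can record a dose as missed.
- SAP Section 6.4.1 imputes AE start and end dates. It does not supply a missing Week 7 dose date.
- SAP Section 11 puts every safety analysis on the Safety Set, and Section 11.1 makes no exception. These subjects therefore stay in the denominator by default.
- SAP Section 6.2 names SAS, where a missing date sorts below any real date. A literal test that the AE date exceeds the cut-off is then true for every event of such a subject, including those from Weeks 1-6. If the program first requires a non-missing cut-off, none is counted.

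**4. Subjects without a cut-off, size**

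Number = 250 x share. The share is an assumption: SAP Section 5.3 only calls more than 5% stopping before six weeks for non-AE reasons higher than expected, and no AE-related rate is given.
- 5%: 12.5 per arm.
- 10%: 25 per arm.
- 15%: 37.5 per arm.

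**5. Do the visit-based summaries close the gaps?**

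They normally include Day 43. The Week 6 visit is Day 42 ±1, however, so a window opening one day later can start on Day 42, 43 or 44. One summary covers Week 7 only and the other ends at last dose. Neither captures later events in early stoppers.

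**The case against.** A reader might infer that all the after-Week-6 tables undercount events and that this biases the B versus C comparison. On that reading, with a true incidence of 30% and 5%, 10% or 15% of subjects without a cut-off, the tables would show 30% x 0.95 = 28.5%, 30% x 0.90 = 27.0% or 30% x 0.85 = 25.5%. The documents do not support this, for four reasons.

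- The second definition keeps unresolved switch-day events, and the two visit-based summaries normally include that day. Only the onset-only tables are certain to lose it.
- The SAP gives no rule for subjects without a cut-off, and an unspecified case is not an exclusion. Events could as easily be over-included.
- Arms B and C receive the same blinded treatment up to Week 6. The share without a cut-off should differ between them only by chance.
- The 30% and the 5-15% are not in the documents. The calculation also assumes that every event is lost and that early stoppers have the same later incidence as others. Some will have left the study altogether and have no later events to lose.

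It is also fair to say that safety is descriptive: SAP Section 11 plans no tests between arms. That limits the weight of the point. It does not supply the missing rule, and it does not explain why the cut-off is strict here but inclusive at first dose.

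**Conclusion.** Two drafting gaps stand. The onset-only tables exclude events starting on the switch day, and no after-Week-6 definition says what to do with a subject who lacks a Week 7 Day 1 dose.

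Both are minor. The switch-day loss is about one or two events per hundred over the longer windows. It matters mainly for the first week after the switch, where one day is a seventh of the window under uniform onset. The missing cut-off is potentially the larger gap, but neither its size nor its direction can be settled from the documents. It bears more on absolute rates and on contrasts with placebo than on B versus C, because pre-Week-7 stopping may differ between active drug and placebo but is not expected to differ between Arms B and C. Efficacy, type I error and sample size are not affected.

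**What to change.** In SAP Section 11.1, for both after-Week-6 definitions and every table that refers back to them:

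- Replace the strict date rule with an inclusive one: an event counts if it starts on or after the date and time of the first Week 7 dose. Use the same cut-off for the ongoing clause.
- When that dose is missing or was not taken, use Study Day 43, that is, first dose date + 42 days.
- Say how an event on the cut-off date with no recorded onset time is treated. The CRF question that settles this at first dose has no stated counterpart at Week 7.

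Keep the Safety Set as denominator. Restricting it to subjects still in the study at Day 43 would replace the planned set with a post-randomization subset. That count can be shown alongside for context. The visit-based withdrawal summary serves a separate purpose and can stay as it is.

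The cost is SAP wording and a few lines of programming. No new data are needed, and the change should be made before unblinding.
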